Power calculation: For both primary outcomes, we have recalculated the power based on an assumed dropout rate of 10% at 4 weeks after radiotherapy and 15% dropout rate at the one-year follow-up. Hence the power is based on sample sizes of 318 for CRP at 4 weeks and 300 for Urgency Syndrome at 12 months. We have used an alpha of 0.05 for both comparisons. For CRP at 4 weeks, following the results reported in Pal et al [14] we assume that in the control group CRP will increase by 400ng/mL, and that in the intervention group it will decrease by 700ng/mL, with a common SD of 3100. With these assumptions, we will have 88% to detect a difference. For Urgency Syndrome at 12 months, based on results we published in 2019 [15] we assume that at baseline the mean syndrome score will be -2.1 (SD=2.8) in both arms, but will increase during the study to 1.1 (SD=4.6) among the control group. Assuming that the intervention mitigates half of this increase, we estimate that in the intervention group, the mean urgency syndrome score will increase to -0.5 (SD=4.6). Hence the change in the two groups will be 3.2 and 1.6, respectively, with a common SD of 3.6. Under these assumptions, we will have 97% power to detect a difference.

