5. ANALYSIS

5.1. Outcome definitions

5.1.1. Co-Primary outcomes

The co-primary outcome of change in concentration of hypersensitive CRP will be calculated as

$$\text{CRP at four weeks after the end of radiotherapy} - \text{CRP at baseline}$$

Hence, a positive value for the change will indicate an increase in CRP and a negative value will indicate a decrease.

The co-primary outcome of change in urgency syndrome will be calculated as

Urgency Syndrome at one-year after the end of radiotherapy – Urgency Syndrome at baseline

Higher scores of the Urgency Syndrome indicate worse symptoms. Hence a negative value for the change in Urgency score will indicate a worsening of symptoms over the duration of the trial, and a positive value will indicate an improvement in symptoms.

The Urgency Syndrome Score for each participant at each timepoint will be calculated using the factor loadings identified in Steineck et al [5].

All questions related to the urgency factor loadings in the paper by Steineck et al [5] are included in Fidura except one: 'Immediate need to defecate'. The reason is because it was very similar to the variable 'Sudden defecation urgency requiring lavatory'. The new question is on the same scale (1-7) as the old question, and we took the decision to substitute it without further amendments.

The urgency syndrome score for each participant and occasion is based on 14 questions, each of which is scored on a 1-7 scale, where 1 indicates the lowest level of symptoms and 7 the highest.

To calculate the score, first, for each participant and occasion, the variable will be standardized using the formula $X - \mu / \sigma$, where:

- X is the score for that participant for that specific question
- μ is the mean of that specific question from all participants (both arms) at the specific timepoint (baseline or follow-up)
- σ is the standard deviation of all responses (both arms) to that question at that timepoint

Then, each question will be multiplied by a loading factor. Finally, the scores will be summed up to a final score.

| Q # | Question text (translated from Swedish) | Loading factor |
|-----|---|----------------|
| 46 | Loose stools the last 3 months at baseline /the last week, 4 weeks after radiotherapy /the last three months, one-year after radiotherapy | 0.71 |

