5.1.2. Secondary outcomes

Unless otherwise stated, all secondary outcomes will be measured as change from baseline, as described above for the primary endpoints.

Leakage Syndrome

Leakage Syndrome scores will be calculated using the same method described above for Urgency Syndrome. The questions and associated factor loadings are described below:

| Q | Question text (translated from Swedish) | Loading factor |
|----|--|----------------|
| 50 | Without warning leaked feces into the clothes, despite having previously emptied bowels, in the last 3 months at baseline /the last week, 4 weeks after radiotherapy /the last three months, one-year after radiotherapy | 0.68 |
| 51 | Without warning emptied all feces into the clothes in the last 3 months at baseline /the last week, 4 weeks after radiotherapy /the last three months, one-year after radiotherapy | 0.47 |
| 52 | Leakage of loose stools, while awake, in the last 3 months at baseline /the last week, 4 weeks after radiotherapy /the last three months, one-year after radiotherapy | 0.62 |
| 53 | Leakage of loose stools, while asleep, in the last 3 months at baseline /the last week, 4 weeks after radiotherapy /the last three months, one-year after radiotherapy | 0.53 |
| 54 | Leakage of solid stools, while awake, in the last 3 months at baseline /the last week, 4 weeks after radiotherapy /the last three months, one-year after radiotherapy | 0.43 |
| 55 | Leakage of solid stools, while asleep, in the last 3 months at baseline /the last week, 4 weeks after radiotherapy /the last three months, one-year after radiotherapy | 0.34 |
| 60 | Smelled feces the last 3 months at baseline /the last week, 4 weeks after radiotherapy /the last three months, one-year after radiotherapy | 0.52 |

Excessive Gas Discharge Syndrome

Excessive Gas Discharge Syndrome scores will be calculated using the same method described above for Urgency Syndrome. The questions and associated factor loadings are described below:

| Q | Question text (translated from Swedish) | Loading factor |
|----|---|----------------|
| 58 | Not been able to hold gas (farts) in the rectum when needed in the last 3 months at baseline /the last week, 4 weeks after radiotherapy /the last three months, one-year after radiotherapy | 0.79 |

| | | |
|----|--|------|

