| 59 | Audible passing of gas (farts) that you have not been able to stop in the last 3 months at baseline /the last week, 4 weeks after radiotherapy /the last three months, one-year after radiotherapy | 0.81 |
| 60 | Bad-smelling gas emissions (farts) that you have not been able to stop in the last 3 months at baseline /the last week, 4 weeks after radiotherapy /the last three months, one-year after radiotherapy | 0.67 |

Excessive Mucus Discharge Syndrome

Excessive Mucus Discharge Syndrome scores will be calculated using the same method described above for Urgency Syndrome. The questions and associated factor loadings are described below:

| Q | Question text (translated from Swedish) | Loading factor |
|----|--|----------------|
| 64 | Mucus from the intestine in the last three months at baseline the last 3 months at baseline /the last week, 4 weeks after radiotherapy /the last three months, one-year after radiotherapy | 0.7 |
| 65 | Mucus discharge from the rectum, when awake, in the last 3 months at baseline /the last week, 4 weeks after radiotherapy /the last three months, one-year after radiotherapy | 0.81 |
| 66 | Mucus discharge from the rectum, when asleep, in the last 3 months at baseline /the last week, 4 weeks after radiotherapy /the last three months, one-year after radiotherapy | 0.51 |

Blood Discharge Syndrome

Blood Discharge Syndrome scores will be calculated using the same method described above for Urgency Syndrome. The questions and associated factor loadings are described below:

| Q | Question text (translated from Swedish) | Loading factor |
|----|--|----------------|
| 51 | Without warning emptied all feces into the clothes in the last 3 months at baseline /the last week, 4 weeks after radiotherapy /the last three months, one-year after radiotherapy | 0.16 |
| 61 | Blood from the intestine in the last 3 months at baseline /the last week, 4 weeks after radiotherapy /the last three months, one-year after radiotherapy | 0.53 |
| 62 | Leakage of blood from the rectum, while awake, in the last 3 months at baseline /the last week, 4 weeks after radiotherapy /the last three months, one-year after radiotherapy | 0.97 |

| | | |
|----|---|------|
| 63 | Leakage of blood from the rectum, while asleep, in the last 3 months at baseline /the last week, 4 weeks after radiotherapy /the last three months, one-year after radiotherapy | 0.4 |

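### Standardizing each item within its own visit removes change common to both arms, so the syndrome change scores cannot show worsening or improvement over the trial

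*SAP*

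**What the plan says.** SAP 5.1.1 builds the Urgency Syndrome score from 14 items scored 1 to 7. Each item is standardized before weighting: "μ is the mean of that specific question from all participants (both arms) at the specific timepoint (baseline or follow-up"), and "σ is the standard deviation of all responses (both arms) to that question at that timepoint". The weighting follows: "Then, each question will be multiplied by a loading factor. Finally, the scores will be summed up to a final score". The co-primary outcome is the one-year score minus the baseline score. The SAP gives that change an absolute meaning: "Hence a negative value for the change in Urgency score will indicate a worsening of symptoms over the duration of the trial", with a positive value read as improvement.

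SAP 5.1.2 carries the rule over to the secondary outcomes, for example "Leakage Syndrome scores will be calculated using the same method described above for Urgency Syndrome" and "Blood Discharge Syndrome scores will be calculated using the same method described above for Urgency Syndrome". The gas and mucus syndromes are treated alike, and all four are analyzed as change from baseline.

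SAP 2.3 plans on a score that moves over time: "we assume that at baseline the mean syndrome score will be -2.1 (SD=2.8) in both arms", rising to 1.1 in the control group and -0.5 in the intervention group. It concludes: "Hence the change in the two groups will be 3.2 and 1.6, respectively, with a common SD of 3.6".

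**The concern.** Subtracting each visit's own both-arm mean from every item takes out whatever happened to the cohort as a whole between the two visits. What remains is each patient's position relative to everyone else at that visit. A difference between two such positions is not a change in symptoms. Three consequences follow.

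- An arm that truly worsened, but less than the other arm, appears to improve.
- A patient who gives identical answers at both visits can receive a non-zero change.
- Arm-level changes have no absolute meaning, so prevention of worsening cannot be told apart from improvement.

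Shared worsening is the expected case here: SAP 1.1 opens by saying that nearly all of these patients end up with lasting changes in bowel habits, and 2.3 assumes that both arms get worse. One co-primary outcome and all four secondary outcomes are affected.

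The sentence in 5.1.1 that interprets the change also has its sign reversed, since higher scores are worse and the change is follow-up minus baseline. That is a separate error, and correcting the sign does not cure this one.

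**Working it through.** **The plan's own power figure.** Inputs from SAP 2.3: difference 3.2 - 1.6 = 1.6, SD of change 3.6, N = 300, alpha 0.05 (taken as two-sided). With 150 per arm, the standard error is 3.6 × √(2/150) = 0.416 and 1.6/0.416 = 3.85. Power is Φ(3.85 - 1.96) = 97.1%, or 97.0% with the t distribution. Splitting 300 in the achieved ratio 190:164 (161 and 139) gives 96.9%. The stated 97% reproduces, and it uses only the difference and the SD.

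**Pooled mean of the score.** The printed formula lacks brackets; since the text speaks of standardizing, it is read as (X - μ)/σ. For patient i, item j, visit t and loading L, the score is S(i,t) = Σj Lj (X(i,j,t) - μ(j,t))/σ(j,t). Averaging over the patients used to compute μ gives Σj (Lj/σ(j,t)) × (μ(j,t) - μ(j,t)) = 0 at every visit. The pooled change is exactly 0 when the same people answer at both visits. With dropout it departs from 0 only through who left.

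**Planning means against that constraint.**

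- Baseline: both arms are at -2.1, so the pooled mean is -2.1, where the rule forces 0.
- One year, equal arms: (150 × 1.1 - 150 × 0.5)/300 = 0.30.
- One year, 190 control and 164 fiber: (209 - 82)/354 = 0.36. With 164 and 190: (180.4 - 95)/354 = 0.24.
- Pooled change: 0.30 + 2.1 = 2.40 (2.34 to 2.46), where the rule forces about 0.

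**What would be reported under those assumptions.** Assume the 1.6 difference carries over to the visit-centred scale. Both arms are then 0 at baseline. At one year, control is 1.1 - 0.30 = +0.80 and fiber is -0.5 - 0.30 = -0.80 (sizes 0.74 to 0.86 with unequal arms). Assumed changes of +3.2 and +1.6 become about +0.8 and -0.8.

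**A patient with identical answers.** If item SDs do not change, the score change is -Σj Lj (μ(j,1) - μ(j,0))/σj, which is minus the cohort's shift. In planning units this is about -2.4 (-2.34 to -2.46), or 2.4/1.6 = 1.5 times the assumed treatment difference.

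**Simulation.** The item distributions are assumed, because the SAP gives none. There were 14 ordinal items driven by one latent factor, the SAP loadings (sum 5.72), 190 and 164 randomized, 15% random dropout and 1,000 replicates per scenario. The analysis regressed change on arm, site and baseline score. The fixed rule uses one mean and SD per item, pooled over arms and both visits.

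| Truth (latent shift, control/fiber) | Mean change, SAP rule | Mean change, fixed rule | Rejection, SAP vs fixed |
|---|---|---|---|
| Both worsen (0.8/0.4) | +0.42 / -0.49 | +1.86 / +0.88 | 86.8% vs 86.9% |
| Only control worsens (0.4/0) | +0.42 / -0.48 | +0.93 / +0.01 | 87.4% vs 87.3% |
| Only fiber improves (0/-0.4) | +0.40 / -0.46 | 0.00 / -0.84 | 86.2% vs 86.3% |
| Both worsen equally (0.6/0.6) | -0.01 / +0.01 | +1.36 / +1.37 | 4.1% vs 4.0% |

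The first three situations are clinically different but look nearly the same under the SAP rule. With no shift in either arm, type I error was 5.9% vs 6.0%. A second simulation, with other assumed items and baseline values as the fixed reference, agreed: with two worsening arms, the SAP rule gave +1.33 and -1.33 where the fixed reference gave +6.0 and +2.9.

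**The case against.** The strongest reply is that the planned inference survives. The objective and the superiority framework compare fiber with placebo. SAP 5.2 fits one regression with baseline score as a covariate, so the treatment coefficient is the same whether the outcome is the change or the one-year score, and the centring constant goes into the intercept. This stands: rejection rates barely move and the 97% is arithmetically sound. The effect is, however, expressed in units set by the one-year item SDs.

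Second, the SAP has no table or test for within-arm syndrome changes, so the misreading may never be printed. This stands in part. But the SAP defines the outcome as a change and says in words what its sign means over time, and arm means are commonly reported beside a treatment effect.

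Third, the +0.8/-0.8 and -2.4 figures are conditional. They carry planning units to another scale, and the second also needs stable item SDs, for which a planned score SD rising from 2.8 to 4.6 gives no support. This stands; they illustrate size. The zero pooled mean needs no such assumption.

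Fourth, a pooled reference is one choice among several and its units also depend on the data. In the first simulation, for the same latent difference of 0.4, the adjusted effect ran from -0.86 to -0.92 under the SAP rule and from -0.84 to -0.98 under the pooled rule. This too stands: the case for a fixed reference is that change over time becomes readable, not that the effect estimate becomes more stable.

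**Conclusion.** The concern holds. As written, the scoring rule makes the both-arm mean score 0 at each visit, so the change cannot carry the meaning that 5.1.1 gives it, whichever sign is used. The means and changes in 2.3 cannot arise on that score. Both conclusions are algebra, apart from reading the formula as (X - μ)/σ and allowing for dropout selection.

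Under the plan's own planning figures, and if the 1.6 difference carries over, a fiber arm assumed to worsen by 1.6 would be shown improving by about 0.8. One co-primary and four secondary outcomes are affected as descriptions of what happened to patients. The treatment test, its type I error and the arithmetic of the 97% power are essentially untouched, although the power inputs come from a differently scaled score. This should be fixed before unblinding, but it does not threaten the main comparison.

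**What to change.** For all five syndromes, standardize every occasion with one fixed mean and SD per item: the values pooled over both arms and over baseline and one year, computed before unblinding. Baseline values alone, or those of the cohort behind the loadings, would also be fixed references. Pooling is preferred to baseline alone because an item with almost no spread at baseline would get an unstable or undefined weight. Print the formula with brackets, and restate how the change is read so that it agrees with higher scores being worse.

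In 2.3, state that the planning means come from a differently scaled score, and that the power rests only on the difference of 1.6 and the SD of 3.6, taken as assumptions on the new scale.

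If the visit-specific rule is kept, the least that is needed is to delete the reading of change over time, to state that only the between-arm difference is interpretable, and to add the note to 2.3.

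The cost is small: SAP wording and scoring code, with no new data and no change to the regression. The fix has limits. The effect moves to a different numerical scale, and the planning means still do not fit it: over both visits they pool to (-2.1 + 0.30)/2 = -0.9, not 0. Very rare items are not cured either. As an illustration, a single answer of 2 among 354 answers of 1 has z = 18.8, and two among 654 pooled answers have z = 18.0.

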5.1.2. Secondary outcomes

Unless otherwise stated, all secondary outcomes will be measured as change from baseline, as described above for the primary endpoints.

Leakage Syndrome

Leakage Syndrome scores will be calculated using the same method described above for Urgency Syndrome. The questions and associated factor loadings are described below:

| Q | Question text (translated from Swedish) | Loading factor |
|----|--|----------------|
| 50 | Without warning leaked feces into the clothes, despite having previously emptied bowels, in the last 3 months at baseline /the last week, 4 weeks after radiotherapy /the last three months, one-year after radiotherapy | 0.68 |
| 51 | Without warning emptied all feces into the clothes in the last 3 months at baseline /the last week, 4 weeks after radiotherapy /the last three months, one-year after radiotherapy | 0.47 |
| 52 | Leakage of loose stools, while awake, in the last 3 months at baseline /the last week, 4 weeks after radiotherapy /the last three months, one-year after radiotherapy | 0.62 |
| 53 | Leakage of loose stools, while asleep, in the last 3 months at baseline /the last week, 4 weeks after radiotherapy /the last three months, one-year after radiotherapy | 0.53 |
| 54 | Leakage of solid stools, while awake, in the last 3 months at baseline /the last week, 4 weeks after radiotherapy /the last three months, one-year after radiotherapy | 0.43 |
| 55 | Leakage of solid stools, while asleep, in the last 3 months at baseline /the last week, 4 weeks after radiotherapy /the last three months, one-year after radiotherapy | 0.34 |
| 60 | Smelled feces the last 3 months at baseline /the last week, 4 weeks after radiotherapy /the last three months, one-year after radiotherapy | 0.52 |

Excessive Gas Discharge Syndrome

Excessive Gas Discharge Syndrome scores will be calculated using the same method described above for Urgency Syndrome. The questions and associated factor loadings are described below:

| Q | Question text (translated from Swedish) | Loading factor |
|----|---|----------------|
| 58 | Not been able to hold gas (farts) in the rectum when needed in the last 3 months at baseline /the last week, 4 weeks after radiotherapy /the last three months, one-year after radiotherapy | 0.79 |

| | | |
|----|--|------|
| 59 | Audible passing of gas (farts) that you have not been able to stop in the last 3 months at baseline /the last week, 4 weeks after radiotherapy /the last three months, one-year after radiotherapy | 0.81 |
| 60 | Bad-smelling gas emissions (farts) that you have not been able to stop in the last 3 months at baseline /the last week, 4 weeks after radiotherapy /the last three months, one-year after radiotherapy | 0.67 |

Excessive Mucus Discharge Syndrome

Excessive Mucus Discharge Syndrome scores will be calculated using the same method described above for Urgency Syndrome. The questions and associated factor loadings are described below:

| Q | Question text (translated from Swedish) | Loading factor |
|----|--|----------------|
| 64 | Mucus from the intestine in the last three months at baseline the last 3 months at baseline /the last week, 4 weeks after radiotherapy /the last three months, one-year after radiotherapy | 0.7 |
| 65 | Mucus discharge from the rectum, when awake, in the last 3 months at baseline /the last week, 4 weeks after radiotherapy /the last three months, one-year after radiotherapy | 0.81 |
| 66 | Mucus discharge from the rectum, when asleep, in the last 3 months at baseline /the last week, 4 weeks after radiotherapy /the last three months, one-year after radiotherapy | 0.51 |

Blood Discharge Syndrome

Blood Discharge Syndrome scores will be calculated using the same method described above for Urgency Syndrome. The questions and associated factor loadings are described below:

| Q | Question text (translated from Swedish) | Loading factor |
|----|--|----------------|
| 51 | Without warning emptied all feces into the clothes in the last 3 months at baseline /the last week, 4 weeks after radiotherapy /the last three months, one-year after radiotherapy | 0.16 |
| 61 | Blood from the intestine in the last 3 months at baseline /the last week, 4 weeks after radiotherapy /the last three months, one-year after radiotherapy | 0.53 |
| 62 | Leakage of blood from the rectum, while awake, in the last 3 months at baseline /the last week, 4 weeks after radiotherapy /the last three months, one-year after radiotherapy | 0.97 |

| | | |
|----|---|------|
| 63 | Leakage of blood from the rectum, while asleep, in the last 3 months at baseline /the last week, 4 weeks after radiotherapy /the last three months, one-year after radiotherapy | 0.4 |
| 65 | Mucus discharge from the rectum, when awake, in the last 3 months at baseline /the last week, 4 weeks after radiotherapy /the last three months, one-year after radiotherapy | 0.18 |
| 67 | Itching in the anus during the last 3 months at baseline /the last week, 4 weeks after radiotherapy /the last three months, one-year after radiotherapy | 0.15 |
| 68 | Pain in the anus during the last 3 months at baseline /the last week, 4 weeks after radiotherapy /the last three months, one-year after radiotherapy | 0.14 |

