1.2.2. Secondary Objectives

Secondary Objective 1: Investigate if the addition of 6 g psyllium husk, compared to placebo, will affect the level of Leakage Syndrome, measured one year after the end of radiotherapy

Secondary Objective 2: Investigate if the addition of 6 g psyllium husk, compared to placebo, will affect the level of Excessive Gas Discharge Syndrome, measured one year after the end of radiotherapy

Secondary Objective 3: Investigate if the addition of 6 g psyllium husk, compared to placebo, will affect the level of Excessive Mucus Discharge Syndrome, measured one year after the end of radiotherapy

Secondary Objective 4: Investigate if the addition of 6 g psyllium husk, compared to placebo, will affect the level of Blood Discharge Syndrome, measured one year after the end of radiotherapy

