| 47 | Returned to the toilet within one hour after defecation to again empty the bowel the last 3 months at baseline /the last week, 4 weeks after radiotherapy /the last three months, one-year after radiotherapy | 0.61 |

| | | |
|----|--|------|
| 48 | Sudden bowel movements that required an immediate visit to the toilet in the last 3 months at baseline /the last week, 4 weeks after radiotherapy /the last three months, one-year after radiotherapy | 0.85 |
| 49 | Time to hold bowel movements during the last 3 months at baseline /the last week, 4 weeks after radiotherapy /the last three months, one-year after radiotherapy | 0.69 |
| 50 | Without warning leaked feces into the clothes, despite having previously emptied bowels, in the last 3 months at baseline /the last week, 4 weeks after radiotherapy /the last three months, one-year after radiotherapy | 0.35 |
| 51 | Without warning emptied all feces into the clothes in the last 3 months at baseline /the last week, 4 weeks after radiotherapy /the last three months, one-year after radiotherapy | 0.26 |
| 52 | Leakage of loose stools, while awake, in the last 3 months at baseline /the last week, 4 weeks after radiotherapy /the last three months, one-year after radiotherapy | 0.40 |
| 53 | Leakage of loose stools, while asleep, in the last 3 months at baseline /the last week, 4 weeks after radiotherapy /the last three months, one-year after radiotherapy | 0.22 |
| 57 | Felt bloated for the last 3 months at baseline /the last week, 4 weeks after radiotherapy /the last three months, one-year after radiotherapy | 0.32 |
| 58 | Not been able to hold gas (farts) in the rectum when needed in the last 3 months at baseline /the last week, 4 weeks after radiotherapy /the last three months, one-year after radiotherapy | 0.25 |
| 60 | Bad-smelling gas emissions (farts) that you have not been able to stop in the last 3 months at baseline /the last week, 4 weeks after radiotherapy /the last three months, one-year after radiotherapy | 0.27 |
| 67 | Itching in the anus during the last 3 months at baseline /the last week, 4 weeks after radiotherapy /the last three months, one-year after radiotherapy | 0.23 |
| 68 | Pain in the anus during the last 3 months at baseline /the last week, 4 weeks after radiotherapy /the last three months, one-year after radiotherapy | 0.22 |
| 69 | Abdominal pain the last 3 months at baseline /the last week, 4 weeks after radiotherapy /the last three months, one-year after radiotherapy | 0.34 |

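### Question 60 is a fecal-odour item in the Leakage table but a gas item in the Urgency and Gas tables, so at least one number or text is wrong

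*SAP*

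**What the plan says.** SAP section 5.1.1 standardizes each question and then states: "Then, each question will be multiplied by a loading factor. Finally, the scores will be summed up to a final score". For the first secondary outcome, section 5.1.2 adds: "Leakage Syndrome scores will be calculated using the same method described above for Urgency Syndrome". The tables of question number, translated text and loading are therefore the working definition of all five scores.

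Number 60 appears in three of the five tables:

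- **Leakage (5.1.2):** "60 | Smelled feces the last 3 months at baseline", loading 0.52.
- **Urgency (5.1.1):** "60 | Bad-smelling gas emissions (farts) that you have not been able to stop in the last 3 months at baseline", loading 0.27.
- **Excessive Gas Discharge (5.1.2):** the same text as in Urgency, loading 0.67.

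All three rows are complete. The SAP mentions no sub-items and no second questionnaire version that would explain the difference. It names no database variables.

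**The concern.** Smelling of feces and being unable to hold back foul-smelling gas are different symptoms, yet both carry the same number. Besides a translated text, the number is the only link the tables give between a loading and the trial data.

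A programmer who selects items by number would put the gas item into the Leakage score with a loading meant for fecal odour. Leakage is the outcome of Secondary Objective 1, which asks whether psyllium "will affect the level of Leakage Syndrome, measured one year after the end of radiotherapy". The Leakage score would then also share an item with the Gas score, another secondary outcome. A programmer who selects by text would get a different Leakage score. As written, the definition does not say which is meant.

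**Working it through.** **Step 1: is number 60 an isolated case?** The five tables hold 14 (Urgency) + 7 (Leakage) + 3 (Gas) + 3 (Mucus) + 7 (Blood) = 34 rows. Nine numbers occur in more than one table:

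| Number | Loadings by table | Second-highest loading | Same text throughout? |
|---|---|---|---|
| 50 | Leakage 0.68, Urgency 0.35 | 0.35 | yes |
| 51 | Leakage 0.47, Urgency 0.26, Blood 0.16 | 0.26 | yes |
| 52 | Leakage 0.62, Urgency 0.40 | 0.40 | yes |
| 53 | Leakage 0.53, Urgency 0.22 | 0.22 | yes |
| 58 | Gas 0.79, Urgency 0.25 | 0.25 | yes |
| **60** | **Gas 0.67, Leakage 0.52, Urgency 0.27** | **0.52** | **no** |
| 65 | Mucus 0.81, Blood 0.18 | 0.18 | yes |
| 67 | Urgency 0.23, Blood 0.15 | 0.15 | yes |
| 68 | Urgency 0.22, Blood 0.14 | 0.14 | yes |

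Only number 60 changes its text.

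**Step 2: which entry is wrong?** There are two main readings.

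1. *Two items, one misnumbered.* The Leakage row is then the likelier error. Two tables agree against it, the gas items run 58 to 60, and 56 is the only number from 46 to 69 that no table uses, directly after the leakage items 50 to 55. This does not show that 56 is the right number.
2. *One Swedish item, translated in two ways.* Then only a text is wrong. This looks less likely. Number 60 would be the only item shared by Leakage and Gas, and its second-highest loading would be 0.52, against 0.14 to 0.40 for the other eight.

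The questionnaire is not shown, so this ranking is inference. On either reading at least one entry is wrong.

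**Step 3: share of each score's loadings carried by number 60.**

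- Leakage: the loadings 0.68 + 0.47 + 0.62 + 0.53 + 0.43 + 0.34 + 0.52 sum to 3.59; 0.52/3.59 = 14.5%.
- Urgency: the 14 loadings sum to 5.72; 0.27/5.72 = 4.7%.
- Gas: 0.79 + 0.81 + 0.67 = 2.27; 0.67/2.27 = 29.5%.

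The Leakage figure is the likeliest case. The other two apply only if both agreeing tables are wrong.

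**Step 4: how far would a wrong item move the Leakage score?** The SAP gives no item correlations. Assume standardized items that all correlate equally at ρ, the wrong item included. For the score at one occasion:

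- Var = Σw² + ρ[(Σw)² − Σw²], with Σw² = 1.9195 and (Σw)² = 3.59² = 12.8881, so Var = 1.9195 + 10.9686ρ.
- Correlation of right and wrong score = 1 − 0.52²(1 − ρ)/Var = 1 − 0.2704(1 − ρ)/Var.

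| ρ (assumed) | Var | Correlation |
|---|---|---|
| 0.1 | 3.016 | 1 − 0.2434/3.016 = 0.919 |
| 0.3 | 5.210 | 1 − 0.1893/5.210 = 0.964 |
| 0.6 | 8.501 | 1 − 0.1082/8.501 = 0.987 |

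If the gas item is instead taken as uncorrelated with every leakage item, the same three values of ρ give about 0.91, 0.95 and 0.97. These figures describe the score at one occasion. The correlation of the change scores, which are what is analysed, would also need correlations over time that the SAP does not give.

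**The case against.** The strongest reply is that this is an editorial slip. Any numerical effect in the likeliest case needs three things together: two distinct items, an error in the Leakage number rather than its text, and code that selects by number and ignores the text. Even then one of four secondary scores changes, and only slightly. The SAP also offers a tie-breaker: the Urgency loadings come from a cited factor analysis, Leakage is scored by the same method, and the printed text shows which item was meant. Other explanations exist too, such as unlabelled sub-items or different questionnaire versions. The cross-loading argument is only suggestive: 0.67² + 0.52² + 0.27² = 0.79, which one item could carry if the factors are orthogonal, a point on which the SAP is silent.

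Much of this stands. The effect is probably small, the Urgency and Gas cases are remote, and the ranking of the readings is not proof. The contradiction remains. An unlabelled sub-item or version would still leave the printed number unable to identify one item. The cited source can help with the repair, but nothing in the SAP itself reconciles number and text. Nor does the SAP say whether the code follows one or the other.

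**Conclusion.** The point holds: number 60 carries two incompatible texts, and the Leakage score cannot be reproduced unambiguously from the SAP. That much is certain from the document. Whether any result changes is not.

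In the likeliest case a wrong item carries 14.5% of the Leakage loadings, and the score at one occasion still correlates about 0.91 to 0.99 with the correct one across the assumed item correlations. If the two texts translate one item, or the code already uses the right variables, no score changes. No direction of bias is claimed, and sample size and power are not affected. The inconsistency should be corrected because it sits in the definition of a named secondary outcome, not because a large effect is expected.

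**What to change.** Before any scoring:

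1. Check number 60 in the Leakage, Urgency and Gas tables against the Swedish questionnaire and the source factor loadings.
2. Correct whichever number or text is wrong. Do not assume that the unused number 56 is the answer.
3. Add the database variable name to each row of the scoring tables, so that each loading is tied to one variable.
4. Confirm that the scoring code uses the reconciled items.

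The cost is one or two corrected table entries, an added column of variable names and a short code check. The design, sample size and analysis models stay as they are. Settling this before scoring also avoids a choice of items after results are known.
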